Appendix V	Laboratory parameters, normal values
Appendix VI	CBO-directive “Richtlijn Voorzorgsmaatregelen bij jodiumhoudende contrastmiddelen”, page 23-26
Appendix VII	EORTC questionnaire QLQ-C30 + QLQ-LMC21 (colorectal liver metastases module)
Appendix VIII	IDMC charter
Appendix IX	Patient Information (including informed consent)
Appendix X	Monitoring plan
Appendix XI	Investigational Medical Device Dossier (IMDD)
Appendix XII	Toxicity chart HEPAR I trial vs.2, 12-01-12)
Appendix XIII	Summary of standard treatment options for patients with liver Metastases
Appendix XIV	ACR Manual on Contrast Media Version 9 (2013) – Table 3

LIST OF ABBREVIATIONS AND RELEVANT DEFINITIONS

¹⁶⁶ Ho-PLLA-MS	Holmium-166 loaded poly(L-lactic acid) microspheres
¹⁶⁶ Ho-RE	Holmium-166 radioembolization
5-FU/LV	5-fluorouracil in combination with leucovorin
⁹⁰ Y-MS	Yttrium-90 microspheres
⁹⁰ Y-RE	Yttrium-90 radioembolization
µg	Microgram
µmol	Micromole
AE	Adverse Event
ADE	Adverse Device Effect
ALT	Alanine aminotransferase
APTT	Activated partial thromboplastin time
AST	Aspartate aminotransferase
CA	Competent Authority
CBO	Quality institute for Healthcare
CRCLM	Colorectal cancer liver metastases
CRP	C-reactive protein
CT	Computed Tomography
CTCAE	Common Terminology Criteria for Adverse Events
DD	Device Deficiency
e.g.	Exempli gratia
ECG	Electrocardiogram
E-CRF	Electronic Case Report Form
EORTC	European Organization for Research and Treatment of Cancer
EU	European Union
FAS	Full Analysis Set
FDG	Fludeoxyglucose
GBq	Giga Becquerel
GCP	Good Clinical Practice
GMP	Good Manufacturing Practice
Gy	Gray
h	Hour(s)
Hb	Hemoglobin
HCT	Hematocrite
ICH	International Conference on Harmonization
IDMC	Independent Data Monitoring Committee
IEC	Independent Ethics Committee
IGZ	Dutch Health Care Inspectorate
IMDD	Investigational Medical Device Dossier
IU	International Units
i.v.	Intravenous
J	Joule
keV	kilo electron volt
kg	Kilogram
km	Kilometer
L	Liter
LDH	Lactate dehydrogenase
LPFS	Liver specific progression free survival
MBq	Megabecquerel
MCH	Mean corpuscular hemoglobin
MCHC	Mean corpuscular hemoglobin concentration

MCV	Mean corpuscular volume
METC	Medical research ethics committee (MREC) (in Dutch: Medisch Ethische ToetsingsCommissie (METC))
MeV	Mega electron volt
mg	Milligram
ml	Millilitre
MRI	Magnetic Resonance Imaging
MTRD	Maximum Tolerated Radiation Dose
NCA	National Competent Authority
NCI	National Cancer Institute
NLPFS	Non-liver specific progression free survival
NSAIDs	Non-Steroidal Anti-Inflammatory Drugs
NYHA	New York Heart Association
PACS	Picture Archiving and Communication System
PERCIST	PET Response Criteria in Solid Tumours
PES	Post-embolization syndrome
PET	Positron Emission Tomography
PPS	Per Protocol Set
PI	Principal Investigator
PT	prothrombin time
PTC	Protocol
PTT	partial thromboplastin time
QOL	Quality of Life
RDLT	Radiation Dose Limiting Toxicity
RECIST	Response Evaluation Criteria in Solid Tumours
RID	Reactor Institute Delft
RILD	Radiation induced liver disease
SAE	Serious Adverse Event
SADE	Serious Adverse Device Effect
SGOT	Serum glutamate oxaloacetate transaminase
SGPT	Serum glutamate pyruvate transaminase
SI	Système international d'unités (International System of Units)
SPECT	Single Photon Emission Computed Tomography
SVC	Superior vena cava
Sponsor	The sponsor is the party that commissions the organisation or performance of the research, for example a pharmaceutical company, academic hospital, scientific organisation or investigator. A party that provides funding for a study but does not commission it is not regarded as the sponsor, but referred to as a subsidising party.
SUSAR	Suspected Unexpected Serious Adverse Reaction
t	Time
Tc-MAA	Technetium macroaggregates
TLS	Tumour Lysis Syndrome
TT	Thrombin time
ULN	Upper Limit of Normal
UMC	University Medical Center (in Dutch: Universitair Medisch Centrum)
USADE	Unanticipated Serious Adverse Device Effect
VEGF	Vascular Endothelial Growth Factor
VOD	Veno-occlusive disease
Vx2	virus induced papilloma in rabbits liver
WHO	World Health Organization
WMO	Medical Research Involving Human Subjects Act (in Dutch: Wet Medisch-wetenschappelijk Onderzoek met mensen)

SUMMARY

Acronym	Holmium Embolization Particles for Arterial Radiotherapy II – HEPAR II trial
Rationale	A significant need for new treatment options for dominant liver metastases is recognized, because survival of patients with unresectable liver disease is poor. Although ^{90}Y -MS therapy is evermore used and considered a safe and effective treatment option for patients with liver dominant disease, these microspheres have a drawback: following administration the actual biodistribution cannot be accurately visualized and the maximum absorbed radiation dose is relatively low. The preclinical phase and the phase I clinical trial of ^{166}Ho -radioembolization (^{166}Ho -RE) have been successfully completed. In the HEPAR I trial, ^{166}Ho -RE was proven to be a safe treatment. The absorbed radiation dose for ^{166}Ho -MS is 1.5 – 2 times higher than for ^{90}Y -MS. Consequently, a phase II study for evaluation of tumour response is warranted.
Objective	
Primary objective:
 
 To determine target lesions tumour response 
Secondary objectives:
 
 To determine overall tumour response To determine the liver specific progression-free survival To determine non-liver specific progression-free survival To assess overall survival To evaluate toxicity To evaluate quality of life To assess performance status To evaluate $^{99\text{m}}\text{Tc}$-MAA and ^{166}Ho-PLLA-MS scout and therapy dose on SPECT/CT To evaluate ^{166}Ho-PLLA-MS scout dose and ^{166}Ho-PLLA-MS total dose on MRI To evaluate ^{166}Ho-PLLA-MS scout dose and ^{166}Ho-PLLA-MS total dose on PET/CT
Study design	Interventional, treatment, one group, phase II study with a medical device. The study has a group sequential design, with a first decision point when 30 subjects have completed follow-up for three months and further decision points after each 6 patients with 3 months follow-up, up to a maximum of 48 subjects.
Study population	Patients with liver metastases of miscellaneous origin will be included in this study ($n = 30 - 48$). These male and female patients must be aged ≥ 18 years and have dominant liver metastases. All histologies are acceptable, provided no standard therapeutic options are available, such as chemotherapy and surgery.
Intervention	^{166}Ho -PLLA-MS will be administered via a catheter during angiography.

Study endpoints	
Primary endpoint:
 
 • Target lesions tumour response 
Secondary endpoints:
 
 • Overall tumour response • Liver specific progression-free survival post ¹⁶⁶Ho-RE • Non-liver specific progression-free survival • Overall survival • Toxicity • Quality of life • Performance status • ^{99m}Tc-MAA and ¹⁶⁶Ho-PLLA-MS scout and therapy dose SPECT/CTs comparison • ¹⁶⁶Ho-PLLA-MS scout dose and total dose MRI comparison • ¹⁶⁶Ho-PLLA-MS scout dose and total dose PET/CT comparison
Duration of treatment	The study consists of a screening phase of approximately 2 weeks followed by a treatment phase of approximately 2-3 weeks. Patients will be followed until liver specific tumour progression or death has occurred, to a maximum of 12 months.
Methodology	A first cohort of 30 patients will be treated with ¹⁶⁶ Ho-RE. After the first cohort, up to 3 additional cohorts of 6 patients will be treated with ¹⁶⁶ Ho-RE. The total number of patients treated in the HEPAR II trial will therefore be at least 30 and at most 48 patients, depending on the observed number of responses. Early termination at a response interim analysis (after 30, 36 or 42 patients) is determined by pre-defined boundaries on the number of observed responses. The boundary in favour of treatment effect may be crossed before 30 patients are reached, but then the study will continue to at least 30 patients to allow estimation of the key secondary endpoints.
Number of study centers	Single center (UMC Utrecht).
Adverse events	All adverse events will be recorded throughout the study.
Inclusion period	Mar 2012 – Aug 2015
Analysis	
Full analysis will be performed after the last patient's last visit. The primary analysis will be to estimate the target lesions tumour response rate (with 95% confidence interval, adjusted for early stopping if indicated). Secondary analysis will be similar estimations of response rates or estimated survival curves (cumulative incidences). Primary and secondary analyses will be based on the Full Analysis Set; analyses on the Per Protocol Set will also be performed and reported.
 
The study will be monitored with stopping boundaries on the number of observed responses. Early termination may occur as a consequence after 30, 36

	
or 42 subjects completed 3 months follow-up.
 
Safety interim analyses will be performed every 3 months from the moment the first patient has received $^{166}\text{Ho-RE}$. All available follow-up data will be included in the safety evaluation.

Manufacturers of the medical device	
$^{165}\text{Ho-PLLA-MS}$ are manufactured by the radionuclide pharmacy of the UMC Utrecht, The Netherlands.
 
$^{165}\text{Ho-PLLA-MS}$ are neutron activated by the Reactor Institute Delft (Delft, the Netherlands). $^{166}\text{Ho-PLLA-MS}$ doses are prepared by the radionuclide pharmacy of the UMC Utrecht, The Netherlands.

1. INTRODUCTION AND RATIONALE

The liver is the most common site of metastatic spread. As many as 50% of all patients with a primary malignancy will in due course develop hepatic metastases.[1] Metastases confined to the liver most commonly, but not exclusively, occurs from colorectal carcinoma, of which the incidence is very high as well. Each year worldwide approximately one million people develop cancer of the large bowel (colorectal carcinoma).[2] The primary tumour is in general resectable, but unfortunately, in 25% of cases the cancer will have spread to the liver at the time of diagnosis whereas in due time more than 50% of patients will develop hepatic metastases.[3, 4] Subtotal hepatic resection is the treatment of choice, yet only 20-30% of patients are eligible for surgical resection of the liver metastases.[5] If resection is performed with curative intent a 33% 5-year survival is reported.[6] In addition to colorectal cancer, metastasis of other types of malignancy can also be confined to the liver. This comprises breast cancer, neuroendocrine cancers, uveal melanoma, etc. Overall, approximately 70% of all patients with uncontrollable solid malignancy will develop liver metastases.

For several decades, standard first-line chemotherapy for colorectal cancer has consisted of 5-fluorouracil in combination with leucovorin (5-FU/LV). Nowadays, oxaliplatin or irinotecan and the Vascular Endothelial Growth Factor (VEGF) antibody bevacizumab is added to 5-FU/LV which has improved median survival from 12 to about 20 months.[7] Typically, long-term survival for patients with unresectable metastatic disease remains less than 5%. For some other types of cancer, no effective chemotherapy protocol is available at all, e.g. uveal melanoma metastases.[8] A summary of standard treatment options for patients with liver metastases is provided in Appendix XIII.

There is a significant need for additional treatment options for patients with liver metastases who do not exhibit response (anymore) to chemotherapy or who refuse (further) chemotherapy because of severe side effects. An increasingly applied treatment for this category of patients is yttrium-90 radioembolization (⁹⁰Y-RE). ⁹⁰Y-RE consists of injecting radioactive yttrium-90 loaded (glass or resin) microspheres into the hepatic artery through a catheter. A recently performed randomized controlled trial has shown statistically significant improvement in progression-free survival in colorectal cancer liver metastases (CRCLM) patients.[9] ⁹⁰Y-RE is performed in patients with other types of liver metastases as well.[10, 11]

Although yttrium-90 microspheres (⁹⁰Y-MS) therapy is evermore used and considered a safe and effective treatment option for patients with liver dominant disease, these microspheres have a drawback: following administration the actual biodistribution cannot be accurately visualized and the maximum absorbed radiation dose is relatively low. For this reason, holmium-166 loaded poly(L-lactic acid) microspheres (¹⁶⁶Ho-PLLA-MS) have been developed [12, 13] at the Department of Radiology and Nuclear Medicine of the University Medical Center (UMC) Utrecht. Like yttrium-90, holmium-166 emits high-energy beta particles that can eradicate tumours but this isotope also emits gamma radiation which allows for imaging through single photon emission computed tomography (SPECT). In addition, since holmium is highly paramagnetic it can also be visualized *in vivo* using magnetic resonance imaging (MRI). Assessment of the biodistribution of these microspheres is therefore possible. This is very useful for several reasons. Prior to administration of the therapeutic dose a small scout dose of ¹⁶⁶Ho-PLLA-MS can be instilled to predict the distribution of the therapeutic dose. Also, quantitative analysis of the SPECT images allows assessment of the radiation dose delivered on both the tumour(s) and the normal liver (i.e. dosimetry) [14]. Quantitative analysis of the MRI scans is possible as well [15, 16].

In a recent, yet unpublished phantom study by our research group, we found that (a limited number of) 511 keV annihilation photons are emitted during the process of ¹⁶⁶Ho decay. This finding implicates that ¹⁶⁶Ho-MS can be detected with the use of positron emission tomography (PET). The higher resolution of ¹⁶⁶Ho-MS PET compared with ¹⁶⁶Ho-MS SPECT,

might lead to a more accurate biodistribution assessment of $^{166}\text{Ho-MS}$. This may improve the overall predictability and safety of radioembolization. However, the detection qualities of $^{166}\text{Ho-MS}$ PET are still to be investigated in patients. For this reason, we implemented $^{166}\text{Ho-PET/CT}$ imaging in the first 6 patients of the HEPAR II trial.

The pharmaceutical quality of the $^{166}\text{Ho-PLLA-MS}$ has been thoroughly investigated and proven to be satisfactory [17-19]. Several animal studies have been conducted to investigate the intrahepatic distribution (tumour to non-tumour ratio), the toxicity profile/biocompatibility of the $^{166}\text{Ho-PLLA-MS}$, safety of the administration procedure, and efficacy of these particles. A non-survival biodistribution study in rats was performed in which it was demonstrated that the $^{166}\text{Ho-PLLA-MS}$ deposition was restricted to the liver and that in the tumourous tissue the radioactivity concentration was six times higher than in the non-target tissue [20]. To demonstrate that $^{166}\text{Ho-PLLA-MS}$ injected into the hepatic artery have a tumouricidal effect, an efficacy study in virus induced papilloma in rabbits livers (Vx2) was performed. In all animals that were treated with $^{166}\text{Ho-PLLA-MS}$ tumour growth was arrested and necrosis set in [21]. In a rat study, in order to show that $^{166}\text{Ho-PLLA-MS}$ are biocompatible, rods composed of (decayed) $^{166}\text{Ho-PLLA-MS}$ were implanted into the liver and the animals were terminated between 3 days and 18 months post implantation during which time no biochemical or clinical side effects were observed [22]. Finally, an extensive toxicity study in healthy pigs was conducted [23]. Five animals were administered (non-radioactive) $^{165}\text{Ho-PLLA-MS}$ and in 13 animals (radioactive) $^{166}\text{Ho-PLLA-MS}$ were instilled into the hepatic artery. The animals were injected with $^{166}\text{Ho-PLLA-MS}$ in amounts of radioactivity corresponding with very high absorbed liver doses. Just very mild side effects were seen: slight and transitory loss of appetite and somnolence, which may well have been associated with the anesthetic and analgesic agents that had been given and not necessarily with the microsphere 'treatment'. A very important adverse event which had occurred in two animals ($^{166}\text{Ho-PLLA-MS}$) was inadvertent deposition of $^{166}\text{Ho-PLLA-MS}$ into the gastroduodenal artery with consequent radioembolization of the gastric wall. To avoid this type of complication, in analogy to what is already customary in yttrium-90 therapy, selected vessels in patients will be occluded by coiling prior to administration of $^{166}\text{Ho-PLLA-MS}$ [24, 25].

$^{166}\text{Ho-RE}$ has been investigated clinically as well in the HEPAR I trial (Clinicaltrials.gov identifier NCT01031784). In this phase I trial, 15 patients with liver metastases of miscellaneous origin were included, of which 7 with metastases of ocular melanoma, 5 with metastases of colorectal carcinoma, 2 with metastases of cholangiocarcinoma and 1 with metastases of breast cancer.

The study consisted of four radiation dose cohorts (20 Gray (Gy), 40 Gy, 60 Gy and 80 Gy liver absorbed dose). Gy is the 'International System of Units'-unit (SI) of the energy absorbed from ionizing radiation, and equals 1 Joule (J) per kilogram tissue. Cohorts consisted of either three or – in case of serious adverse events – six patients [26]. The 20-Gy cohort was extended to 6 patients because one of the patients developed a pulmonary embolism two weeks after the radioembolization procedure. This complication was attributed to the extended duration of the procedure in this particular patient without any post-procedural prophylactic antithrombotic medication. All following cohorts consisted of 3 patients. Clinical toxicity in the first 3 cohorts comprised mainly symptoms belonging to the post embolization syndrome (PES). PES comprises fatigue, nausea, abdominal pain, fever, vomiting and/or anorexia, and is a known phenomenon in radioembolization treatment. These symptoms were transient in all cases and well-controlled by outpatient medication. Laboratory toxicity was mild except for expected grade 3 liver enzymes toxicity and grade 3 haematological toxicity. Overall, treatment was well tolerated by the patients in the first 3 cohorts (20 Gy – 60 Gy) and the toxicity profile was very similar to the toxicity which is encountered in patients treated with $^{90}\text{Y-RE}$. In the 80-Gy cohort, however, treatment was considerably less well tolerated. Patients had more complaints of abdominal pain and nausea. These symptoms were more severe and lasting longer than the clinical toxicities encountered in the previous cohorts. Furthermore, laboratory toxicity was more severe and in

certain cases progressive with a suspected radiation induced liver disease (RILD) in one patient. Liver toxicity is to some extent intended in radioembolization given the 5-mm reach of the beta emitting holmium. Furthermore, lymphocyte- (up to grade 3), leukocyte- (up to grade 3) and platelet counts (up to grade 4) transiently decreased. These adverse events are most probably caused by activation of hepatic stem cells in the bone marrow due to liver damage [27]. These symptoms are suspected to be related to the higher radiation dose instead of an embolic effect of treatment because the amount of microspheres was equal in all cohorts. This study was not designed to demonstrate efficacy of ¹⁶⁶Ho-RE, but a number of partial remissions and stable disease were observed. A listing of all adverse events encountered in the HEPAR I trial is given in Appendix XIII

The rationale of the study described and proposed in this protocol, the HEPAR II trial, is to assess treatment response in patients with liver dominant disease.

2. OBJECTIVES

In this single center study, the efficacy of radioactive ^{166}Ho -PLLA-MS, a radioembolization device, is tested in patients with liver metastases. A group of at least 30 and at the most 48 patients will undergo radioembolization with ^{166}Ho -PLLA-MS.

Primary objective:

- To determine target lesions tumour response

Secondary objectives:

- To determine overall tumour response
- To determine the liver specific progression-free survival
- To determine non-liver specific progression-free survival
- To assess overall survival
- To evaluate toxicity
- To evaluate quality of life
- To assess performance status
- To evaluate technetium-99m labeled macroaggregated albumin ($^{99\text{m}}\text{Tc}$ -MAA) and ^{166}Ho -PLLA-MS scout and therapy dose on SPECT/CT
- To evaluate ^{166}Ho -PLLA-MS scout dose and ^{166}Ho -PLLA-MS total dose on MRI
- To evaluate ^{166}Ho -PLLA-MS scout dose and ^{166}Ho -PLLA-MS total dose on PET/CT

3. STUDY DESIGN

Study type	Interventional
Study design	Interventional, treatment, one group, phase II study with a medical device.
Study start date	Mar 2012
Estimated study completion date	Aug 2015

This phase II study comprises a group of at least 30 and at the most 48 patients suffering from liver metastases of primary cancers of miscellaneous origin. Patients who will be included have hepatic metastases not amenable for surgical resection or further systemic treatment. A liver absorbed dose of 60 Gy will be used in each patient in this study. A radiation dose of 60 Gy equates to 3.8 GBq ^{166}Ho /kg liver tissue.

The primary outcome is target lesions tumour response at three months follow-up. For this study, this is defined as: 1) complete response on CT at 3 months, or 2) partial response on CT at 3 months or 3) stable disease on Computed Tomography (CT) at 3 months (see chapter 8.3.1 Definition of treatment success).

This single arm open label study will have a sequential design as follows. Patients will be followed for target lesions tumour response up to 12 months or less if liver specific tumour progression or death occurs. Interim analyses for tumour response achieved are based on sequential decision boundaries. Stopping boundaries are determined such that an overall one-side alpha of at the most 0.05 is maintained in case the true tumour response is 20% ($p_0 \equiv 20\%$). Early termination at a response interim analysis (after 30, 36 or 42 patients) is determined by pre-defined boundaries on the number of observed responses. The boundary in favour of treatment effect may be reached or crossed before 30 patients are reached, but then the study will continue to at least 30 patients to allow estimation of the key secondary efficacy endpoints. Early stopping for proven efficacy can only occur after the first 30 patients are evaluated. Boundaries for early stopping due to futility, i.e. absence of a relevant effect on tumour response, are also included, and are in effect even before the number of 30 patients is reached. The sequential design with boundaries as given in Table 1 will have a power of 90% to reach a positive tumour response decision in case the true target lesions tumour response is 40% ($p_1 \equiv 40\%$). The exact overall one sided type I error is 4.5% [28].

Table 1 Stopping boundaries for early termination at interim analysis.[28] Stopping is indicated if the observed number of responses is at the boundary or beyond.

Analysis	Sample Size	Lower Boundary	Upper Boundary
1	30	5	11
2	36	6	13
3	42	7	14
4	48	15	16

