8.4 Independent Data Monitoring Committee (IDMC)

An IDMC is established. The IDMC is an independent group comprising internal members (from within the UMCU) and external members. This phase II study is open label and patients are individually closely monitored for safety, as was done in the HEPAR I study. The main objective is to decide whether or not to embark on a larger phase III trial. Hence it was considered adequate to establish an IDMC with both (independent) internal UMCU members as well as an external member. In case of a future phase III trial, a fully external IDMC is strongly recommended. The IDMC includes the following members:

- Dr. [name], Meander Medical Center Amersfoort; nuclear medicine physician
- Dr. [name], University Medical Center Utrecht; gastro-enterologist
- Dr. [name], Albert Schweitzer ziekenhuis; interventional radiologist
- Dr. [name], Julius Center Health Sciences and Primary Care Utrecht; biostatistician

The IDMC will analyse preliminary study results on tumour response after the first 30 patients who are amenable for tumour response assessment at 3 months (i.e. PPS), and every 6 patients who are amenable for tumour response assessment at 3 months thereafter (see Table 5). Waiting for the three-month follow-up of all 30/36/42/48 patients is only required if, based on the available follow-up in the other patients, it remains uncertain whether the stopping boundaries will be reached.

The IDMC analyse preliminary study results on safety as well (see Table 5). In contrast to the tumour response analyses, the safety analyses will include all patients that received treatment within a time span of 3 months (regardless of their availability for tumour response assessment, i.e. FAS), and therefore, these reviews may not run in sync with the IDMC tumour response analyses. Patient inclusion and treatment may continue during IDMC safety analyses. In its safety analyses, the IDMC will consider specifically the reasons and potential consequences on treatment benefit of the patients that discontinued before the 3 months assessment. The IDMC will receive reports on a regular basis on all SAEs reported for this trial and a complete summary safety report for each safety analysis. The IDMC will work according to the IDMC charter (see Appendix VIII) Recruitment will not be interrupted unless otherwise requested by the IDMC Chairman.

The responsibilities of the IDMC include:

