* IDMC tumour response analyses will be held after the first 30 patients and every 6 patients thereafter. Primarily, patients who are available for tumour response assessment 3 months post treatment are evaluated (PPS). FAS data will be analysed during IDMC reviews of safety

** IDMC safety analyses will be held every 3 months after treatment of the first patient. All patients that received ¹⁶⁶Ho-RE will be evaluated (FAS). Safety analysis will at least be held after treatment of 30 patients.

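### Table 1's futility boundary of 7 at n=42 lets the trial continue with 8 or 9 successes although 16/48 is then out of reach, and the futility rule said to apply before 30 patients has no number

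*Protocol*

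**What the plan says.** Protocol section 3 describes a single-arm group sequential test of the three-month target-lesion response rate. The boundaries are chosen so that "an overall one-side alpha of at the most 0.05 is maintained in case the true tumour response is 20" per cent, and the design "will have a power of 90% to reach a positive tumour response decision in case the true target lesions tumour response is 40" per cent. It adds: "The exact overall one sided type I error is 4.5" per cent.

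Table 1 gives four looks (lower/upper): 5/11 at 30 patients, 6/13 at 36, 7/14 at 42 and 15/16 at 48. The caption makes both boundaries inclusive: "Stopping is indicated if the observed number of responses is at the boundary or beyond". So 7 or fewer at 42 stops for futility, 14 or more stops for efficacy, 8 to 13 continues, and a positive result at 48 needs 16.

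On futility before the first look, section 3 says that the boundaries "are also included, and are in effect even before the number of 30 patients is reached". Section 8.4 (note to Table 5) says "IDMC tumour response analyses will be held after the first 30 patients and every 6 patients thereafter". Sections 2 and 3 and the Summary all describe a trial of at least 30 patients. Section 8.4 also requires waiting for all three-month follow-up only if "it remains uncertain whether the stopping boundaries will be reached", and keeps recruitment open unless the IDMC chair asks otherwise.

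**The concern.** A futility boundary should at least catch every count from which success can no longer be reached. The boundary at 42 misses two such counts. In those cases the efficacy question is already answered negatively, but the written rule sends the trial on to a last cohort of six, each of whom would receive an invasive radioactive treatment. The protocol gives a reason for continuing after a decision is certain (estimating key secondary endpoints) only for reaching 30 patients after the efficacy boundary is crossed. It gives none for going from 42 to 48.

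The sentence on futility before 30 patients is a smaller matter. The IDMC is told that a rule is in force but is given no number to apply, and any stop before 30 would conflict with the stated minimum sample size.

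**Working it through.** **Inputs (Protocol section 3 and Table 1).** Looks at n = 30, 36, 42, 48; lower boundaries 5, 6, 7, 15; upper boundaries 11, 13, 14, 16; both inclusive; p0 = 20%, p1 = 40%.

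**Step 1: reproduce the plan's figures.** An exact binomial recursion carries the distribution of successes from look to look, dropping counts that stop. The probability of crossing the upper boundary is:

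| n | p = 20% | p = 40% |
|---|---|---|
| 30 | 0.02562 | 0.70853 |
| 36 | 0.00484 | 0.06941 |
| 42 | 0.01128 | 0.08989 |
| 48 | 0.00350 | 0.03008 |
| Total | 0.0452 | 0.898 |

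This matches the stated 4.5% and, after rounding, 90%. Exclusive boundaries would give 0.0197 and 0.827, so the inclusive reading is the one intended.

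**Step 2: what can still be reached from n = 42.** The maximum at 48 is x + 6.
- x = 8: 14, below 16.
- x = 9: 15, below 16 and equal to the final lower boundary.
- x = 10: 16, possible only with 6 of 6 (0.4^6 = 0.0041 at p = 40%; 0.2^6 = 0.00006 at p = 20%).

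The earlier looks do not have this defect. The lowest continuing counts, 6/30 and 7/36, can still reach 6 + 18 = 24 and 7 + 12 = 19 at n = 48.

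**Step 3: how often this happens at p = 20%.** The probabilities of continuing at n = 36 with 7, 8 and 9 successes are 0.11089, 0.13357 and 0.11369. For six further patients, P(0) = 0.2621, P(1) = 0.3932 and P(2) = 0.2458.
- P(8 at 42) = 0.11089 × 0.3932 + 0.13357 × 0.2621 = 0.0786
- P(9 at 42) = 0.11089 × 0.2458 + 0.13357 × 0.3932 + 0.11369 × 0.2621 = 0.1096
- Sum = 0.188

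The probability of entering the last stage is 0.4547, so 0.188/0.4547 = 41% of trials that open the last cohort at p0 do so with no chance of success.

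**Step 4: effect of a lower boundary of 9 at n = 42.** No path through 8/42 or 9/42 ends in success, so removing those paths cannot change type I error or power. The recursion confirms 0.045236 and 0.897903 both before and after. The saving in expected N is 6 × P(8 or 9 at 42), if no one is treated beyond 42 while the look is pending.

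| True rate | P(8 or 9 at 42) | E[N], boundary 7 | E[N], boundary 9 | Saving |
|---|---|---|---|---|
| 20% | 18.8% | 38.98 | 37.85 | 1.13 |
| 25% | 14.9% | 41.53 | 40.63 | 0.90 |
| 30% | 7.3% | 40.47 | 40.03 | 0.44 |
| 40% | 0.5% | 33.77 | 33.73 | 0.03 |

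**Step 5: futility before 30.** With x successes in n < 30 assessed patients, the most that can be reached at 30 is x + (30 − n). This is 5 or fewer exactly when n − x ≥ 25, that is, after 25 failures. Such a trial would stop at the n = 30 look in any case, so this rule leaves the 4.5% and 90% untouched. It can act no earlier than the 25th assessed patient.

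**The case against.** Four arguments stand on the other side.

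*The early-decision clause in section 8.4 may already curtail the trial.* At 8 or 9 of 42 the final lower boundary is certain, so on a generous reading no further waiting is needed. But the clause concerns waiting for pending follow-up. It does not say that the last cohort should not be recruited, and the same section keeps recruitment open by default.

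*The IDMC can use judgement.* It includes a biostatistician, weighs all the data, and could advise stopping at 8/42. This mitigates the defect. But section 3 says that early termination is governed by pre-defined boundaries, and discretion does not correct a boundary that is set wrongly.

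*Fewer than six patients would be spared.* This stands. The endpoint takes three months, so part of the last cohort may be treated before patient 42 is assessed. As an assumption, steady accrual of 48 patients over the 42-month inclusion period (March 2012 to August 2015) gives 48/42 × 3 = 3.4 patients per three months. If accrual had to end 12 months before August 2015, it gives 48/30 × 3 = 4.8. Then about 6 − 3.4 = 2.6 or 6 − 4.8 = 1.2 treatments are spared when the event occurs, an average at p0 of 0.188 × 2.6 = 0.49 or 0.188 × 1.2 = 0.23.

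*The pre-30 rule can be worked out.* Section 3 speaks of the efficacy boundary being reached early and contrasts futility with it, which suggests that the n = 30 lower boundary acts as soon as it is certain. That reading is plausible, but no number is written and it still conflicts with the minimum of 30.

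**Conclusion.** The point on the n = 42 boundary holds from Table 1 alone and needs only subtraction. Its size is modest: an 18.8% chance at p0 of opening a last cohort that cannot succeed, falling to 0.5% at the design alternative, and an average saving of at most 1.13 patients at p0. The E[N] figures assume that recruitment pauses at each look.

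The pre-30 sentence is a matter of an unstated number and a conflict with the promised minimum. A reader might infer more from it, namely that the printed 4.5% and 90% hold only if no futility rule operates before 30. The documents do not support this: both figures are correct for Table 1, and both survive curtailment at 25 failures. A reader might also extend the slope of the lower boundary (n/6) to looks at 12, 18 and 24 and find power of 84.2%. But those looks and boundaries appear nowhere in the protocol, which schedules response reviews only from 30, so that figure does not measure a fault in this plan.

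**What to change.** In Table 1, change the lower boundary at n = 42 from 7 to 9. This costs one table cell; type I error, power and the other boundaries stay as they are.

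In section 3, state what futility before 30 means. If curtailment is intended, say that it applies only once 25 failures make 5 or fewer successes in 30 certain, and amend the minimum of 30 patients in the Summary and sections 2 and 3 to allow for it. If no stop before 30 is intended, delete the sentence. Neither choice changes the printed error rates. Any stricter early rule would need its own row in Table 1, a matching review in Table 5 and a restated power.

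It would also help to say in section 8.4 whether recruitment to the last cohort waits for the n = 42 decision, since this determines how many treatments the corrected boundary can spare.
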